## Mechanisms of PNSS-S Effect

Social support for quitting will be assessed using the Partner Interaction Questionnaire, which assesses negative and positive support for quitting. Participants will be instructed to include all forms of support for quitting (including PN support if assigned to the PNSS-S condition). Self-efficacy for smoking cessation will be measured using the Contemplation Ladder, a one-item Likert-type scale (rating 1-10). In participants who set a quit date, adherence to pharmacotherapy will be measured via participant self-report and pharmacy refill report at each study session.

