The primary objective of this project is to examine the feasibility, acceptability and initial efficacy of a peer navigation social support for smoking cessation (PNSS-S) intervention for HIV-positive smokers. We will enroll 78 HIV-positive smokers, regardless of their readiness to quit, into a 24-week randomized pilot study to determine whether enhanced treatment (using a PN to navigate smoking cessation, help obtain medication and treatment, improve adherence to treatment, and provide social support for quitting) will increase quit attempts and smoking cessation rates (measured by 7-day point prevalence) compared with standard care (SC; provider recommendation to quit and quit line referral using the 5A's).

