# Aims

Our specific aims are to examine: (1) the feasibility, acceptability, and initial efficacy of PNSS-S in a 24-week randomized pilot study; (2) to compare the effect of PNSS-S, relative to SC, on mechanisms thought to underlie smoking abstinence in HIV-positive smokers.

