## Methodology

We will adapt an existing, highly effective PN training program that was developed by Co-I [name] to increase engagement in care within the HIV clinic. The PNs for smoking cessation will be former daily smokers who quit smoking and have remained smoke-free for at least two years. We will train the two PNs, enroll 6 HIV-positive smokers to test the intervention, and finalize our protocol. We will refine the PNSS-S based on feedback from the PNs, the 6 participants, and the study nurse. Next, we will conduct a pilot RCT (N = 72) to test the feasibility, acceptability, and initial efficacy of PNSS-S in a randomized, 2-group, repeated measures design. We will randomize 36 HIV-positive smokers to each condition: PNSS-S or standard care (SC). Assessments will be collected at baseline (BL), and at 4-, 12-, and 24-weeks following BL. We will examine the effect of PN on Quitline contact, quit attempts, adherence to pharmacotherapy, smoking cessation rates, 7-day point prevalence abstinence (with biochemical verification), sustained abstinence, self-efficacy for quitting, social support for smoking cessation, study retention and satisfaction. We will calculate a preliminary effect size estimate of PNSS-S on smoking and other secondary outcomes and mechanisms of change. Data will be used to plan a future full-scale RCT.

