## **Baseline Measures of Individual Differences**

Demographics will include age, sex, gender, race, ethnicity, marital status, employment status, income, education level, number of years living with HIV, and history of opportunistic infections. We will obtain most recent CD4 T-cell value and HIV viral load from the MIC medical record (commonly measured in the clinic every 3-6 months). The Fagerström Test for Cigarette Dependence (FTCD) will be administered to evaluate severity of cigarette dependence. An exhaled carbon monoxide (CO) level will be obtained (using a Smokerlyzer ED50 CO meter [Bedfont Scientific, Haddonfield, NJ]), a valid assessment of recent smoking. Participants will provide breath samples for CO at baseline, and each study interview; values of 5 ppm or higher will be considered indicative of smoking. Intention to quit smoking will be assessed using the Smoking Stage of Change questionnaire. Depressive symptoms will be assessed with the Center for Epidemiologic Studies –Depression scale (CES-D).

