Treatment Feasibility, Acceptability, & Efficacy. Individual analyses of variance will be conducted to compare treatments (PNSS-S vs. SC) on the continuous variables of number of sessions attended and client satisfaction scores. For treatment retention rate (dichotomous), a chi-square analysis will be used. Analyses will test the hypothesis that PNSS-S improves point prevalence abstinence relative to SC. Tests of the effect of treatment condition on Quitline usage, quit attempts, and on 7-day point-prevalence abstinence across the 4, 12, and 24 week assessments will be conducted using GEE, which provides appropriate modeling of covariance structures when observations are correlated across time. The primary, between groups, independent variable in the GEE analysis is treatment condition assignment, which will be dummy-coded using SC as the reference group.

Following the intention-to-treat principle, all participants who have been randomized will be included in the analyses.

Potential Mechanisms of PNSS-S Effects. Sample size in this trial precludes formal mediation analysis with adequate power. The analyses are designed to test the plausibility of potential mechanisms of the PNSS-S treatment effect. We will examine change in these variables using multilevel modeling as increased social support and self-efficacy for quitting are important outcomes in and of themselves, which may affect long-term smoking outcomes and will be useful in demonstrating the longer-term effects of PNSS-S. Mediators will be examined separately, rather than simultaneously, given our limited sample size. For each mediator, we will fit a multilevel model to obtain both an initial value (intercept) and rate of change (slope) in each of these variables from baseline to week 4. We will first test whether treatment condition predicts change in these variables. We will then enter the intercept and slope parameters from these models into the main GEE model of smoking outcome to determine whether change in these variables predicts smoking outcomes. We will be able to examine whether the effect of treatment is reduced when the mediator is added to the model and can test for significance (not expected given the sample size) using the products of coefficients method. Social support in the 4 weeks after quitting also will be examined as a potential mediator of PNSS-S effects.

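### Self-efficacy, a named outcome and candidate mediator, is measured only by an item whose name points to readiness to quit; the item wording must be checked and the label or instrument corrected

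*Combined protocol and SAP*

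**What the plan says.** The second aim is "to compare the effect of PNSS-S, relative to SC, on mechanisms thought to underlie smoking abstinence in HIV-positive smokers". Methodology lists among the effects to be examined "self-efficacy for quitting, social support for smoking cessation, study retention and satisfaction". The section Mechanisms of PNSS-S Effect then names one instrument for self-efficacy: "Self-efficacy for smoking cessation will be measured using the Contemplation Ladder, a one-item Likert-type scale (rating 1-10"). It gives no item text, scale anchors or reason for the choice.

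The Data Analysis Plan, under Potential Mechanisms of PNSS-S Effects, gives the variable two roles. As an outcome, it is covered by the statement that "increased social support and self-efficacy for quitting are important outcomes in and of themselves". As a candidate mediator, it is covered by "For each mediator, we will fit a multilevel model to obtain both an initial value (intercept) and rate of change (slope"), with the change taken from baseline to week 4 and both parameters then entered in the main GEE model of smoking.

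Readiness and intention appear separately. The project description says "We will enroll 78 HIV-positive smokers, regardless of their readiness to quit". Baseline Measures of Individual Differences says "Intention to quit smoking will be assessed using the Smoking Stage of Change questionnaire". Under Standard Care Condition, the nurse's session includes an assessment of readiness.

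**The concern.** Self-efficacy here means confidence that one can quit or stay off cigarettes. Contemplation means thinking about quitting. A smoker may be ready to try with little confidence of success, or confident but with no plan to try. A scale named for the second is not, on its face, a measure of the first.

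The distinction matters in this trial because the intervention works on readiness. Participants in the PNSS-S arm who decline to set a quit date discuss quitting as something that unfolds over time, along with the barriers to it, and the peer navigator continues that conversation in later contacts. If the item tracks readiness, the arms could separate on it with no difference in confidence, and the report would say that self-efficacy rose. A gain in confidence without a gain in readiness might not show. Methodology says the data, including preliminary effect sizes for mechanisms of change, will be used to plan a full-scale trial, so a mislabelled mechanism could carry over into that design.

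**Working it through.** No figure in the documents depends on this point, and the plan states no power or sample-size calculation for self-efficacy. The check is therefore a comparison of sections.

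1. **Is self-efficacy part of the planned inference?** Yes. It is on the list of effects in Methodology, it belongs to the second aim, and the Data Analysis Plan treats it both as an outcome and as a candidate mediator.

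2. **How many instruments are named for it?** One. Measures, Baseline Measures of Individual Differences, Feasibility and Acceptability Measures (which includes the efficacy measures) and Mechanisms of PNSS-S Effect name no other self-efficacy or confidence scale. The one instrument has a single item, so no second item or subscale could show what it is picking up.

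3. **What do the documents say the item asks?** Nothing beyond the name, the single item and the 1-10 range. The Assessments section refers to attachments that are not in the supplied text.

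4. **Does the plan itself separate the constructs?** Yes. Readiness is named in the enrolment statement and in the nurse's session, and intention to quit has its own questionnaire. Self-efficacy is listed apart from both.

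5. **What follows?** Two possibilities remain:
   - The Ladder is administered as its name indicates. The construct label is then wrong. The intercept, the slope to week 4, the comparison of arms on change and the mediator term in the GEE model would all describe readiness.
   - A 1-10 confidence item is administered. The analysis is then sound in this respect, and the instrument is misnamed.

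Under either possibility the sentence in Mechanisms of PNSS-S Effect needs correction. Only the first changes what the second aim can conclude.

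6. **How large would the distortion be?** The documents cannot say. They give no correlation between the Ladder and confidence and no expected effect on either, so no attenuation figure is offered.

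**The case against.** The strongest reply is that the documents never describe the Ladder as a readiness measure. They give no wording or anchors, and the attachments that would settle the matter were not supplied. The form may ask about confidence under the wrong name, or the packet may hold another self-efficacy item. The section that assigns intention to the Stage of Change questionnaire does not mention the Ladder, so it shows that the authors separate the constructs, not what this item asks. Part of the work on readiness is also common to both arms, because PNSS-S participants receive the standard-care nurse content as well; only the added discussion and the navigator's contacts differ. Finally, the plan concedes that formal mediation analysis is underpowered and that significance is not expected.

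Most of this stands, and it limits the point. A reader might infer that the self-efficacy result will certainly be a readiness result, or that the trial has no measure of self-efficacy at all. The documents support neither: the first depends on item wording that is not shown, and the second on attachments that are not available.

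The reply does not remove the point. The mismatch rests on the instrument's own name and on the plan's separate handling of readiness and intention. Low power is no defence either, since a larger sample would not turn a readiness item into a confidence item.

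**Conclusion.** The point holds in conditional form. Self-efficacy is paired with a single item whose name indicates a different construct, without item wording or justification and with no other measure named. Either the label or the instrument name has to change. If the item is a readiness item, the plan as written would report a shift in readiness as a shift in self-efficacy, and all the self-efficacy evidence drawn from the named instrument would be affected.

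The reach is small. It covers one variable in an exploratory analysis whose limited power the plan admits. Social support and adherence to pharmacotherapy, the other mechanism variables, have their own measures. A reader might take the point as a threat to the trial's main result. It is not one: abstinence, feasibility, the GEE comparison of the arms on abstinence and the sample of 72 do not use this score.

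The conclusion assumes that the scale's name reflects its content and that no other confidence measure is in the attachments. Checking the forms settles both.

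**What to change.** First read the administered form, confirm whether the packet holds any other confidence item, and state the item wording and anchors in Mechanisms of PNSS-S Effect. Then:

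- **If the item asks about readiness:** add one 1-10 rating of confidence in being able to quit, at the same visits as the Ladder. Use that rating wherever the Data Analysis Plan refers to self-efficacy, in both the week-4 change model and the GEE model. Keep the Ladder and analyse it as readiness to quit.
- **If it asks about readiness and no item can be added,** for instance because data collection has started: rename the variable readiness to quit in Methodology, Mechanisms of PNSS-S Effect and the Data Analysis Plan, and drop the self-efficacy claim.
- **If it already asks about confidence:** correct the instrument's name and leave the analysis as it is.

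The first option costs a wording amendment and one extra paper item per visit, at most four answers per participant if the Ladder is given at baseline and at weeks 4, 12 and 24. The second costs wording and one exploratory claim. The third costs wording only.

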## **Description and Purpose of the Project**

Current smoking prevalence among persons living with HIV (PLWH), is high (40%) compared to the general U.S. population, where smoking prevalence is approximately 15%. Several studies have suggested that PLWH lose more years due to smoking than to HIV infection itself. However, smoking cessation studies in PLWH to date have demonstrated disappointing outcomes, with low quit rates, poor adherence to therapy, and a lack of sustained abstinence. While most HIV-positive smokers report a strong desire to quit, many are unable to do so, and low cessation rates are reported. Considering their high levels of nicotine dependence and low guit rates, HIV-positive smokers may require additional support for quitting compared with the general population of smokers, as they may not only have more smokers in their social network but also may smoke to cope with social isolation related to living with HIV. Peer navigators (PNs) have been used for many years in the field of HIV to support entry and retention in care, and adherence to ART. Linking HIV-positive smokers with PNswho are already embedded within most HIV community care settings—to support access to and utilization of existing smoking cessation resources represents a novel and sustainable approach to encouraging smoking cessation and providing the additional support these smokers may need to make a quit attempt and achieve and sustain abstinence. For example, a PN may encourage the smoker to set a quit date, adhere to smoking cessation medication therapy, utilize the many available smoking cessation resources (e.g., Quitline's, web-based smoking cessation, text messaging support, and local group counseling), and achieve, maintain, or regain abstinence after a smoking lapse. Applying this approach to smoking cessation within the HIV clinic seems to be an untapped resource for improving smoking cessation rates in HIV-positive smokers.

[figure not shown]

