#### Standard Care Condition (SC)

Participants in the SC condition will meet for a 30-minute session with a study nurse. This session will be consistent with standard guidelines for brief advice for smoking cessation based on the 5A's. The nurse will ask about current smoking habits, advise the participant to quit, assess readiness to quit, assist by providing resources (community programs, Quitline phone number), and arrange follow-up. The nurse will calculate and provide personalized feedback about the participants' Lung Age, which provides an estimate of the age at which the FEV1 would be considered normal. This will serve as a motivation tool to encourage smokers to quit and has been shown to increase the odds of quitting. Those willing to set a quit date will be instructed to call their physician for cessation medication and will be provided with the National Cancer Institute (NCI) self-help pamphlet entitled *Clearing the Air* and the *smokefree.gov* website address. Brief treatment is consistent with the

minimum standard of care recommended by the Agency for Health Research and Quality (AHRQ) panel to address smoking cessation treatment. Those participants not willing to set a quit date will be instructed to contact their MD when they are ready.

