## Peer Navigation Social Support for Smoking Cessation Condition (PNSS-S)

Participants in the PNSS-S condition will also meet for a 30-minute session with the study nurse. The nurse will discuss the same content that was provided in the SC condition. In addition (for the PNSS-S condition participants only), the nurse will discuss the importance of social support for guitting and will explain the role of a Peer Navigator (PN). The nurse will then introduce the participant to his/her assigned PN. Finally, the nurse will ask if the participant is ready to set a quit date. Participants who set a quit date will choose the appropriate medication in collaboration with their clinic physician. PNs and nurses will reinforce adherence to the chosen medication. Participants will be informed of the efficacy of pharmacotherapy for smoking cessation. The PN will act as an intermediary between the patient and physician - facilitating the acquisition of the medication by coordinating with the participant's MD for a prescription, reviewing the formulary for medication coverage, ensuring that the prescription is picked up at the pharmacy, and managing any side effects via MD/nurse consultation (similar to their role in improving ART adherence). The PN will also assume the role of providing social support for quitting via weekly phone calls with the participant for 12 weeks. The PN will be well versed with local groups and resources, so that they can direct their participants to the most appropriate services/resources, if the participant is interested. Participants not willing to set a quit date at the time of the nurse visit will be engaged in a discussion of "quitting as a process" and will be encouraged to discuss barriers to quitting. This discussion will continue in contacts with the PN over the coming weeks.

In total, participants randomized to PNSS-S will receive a 30-minute session with the nurse, a quit-day counseling call from the PN (as appropriate), and weekly calls from the PN to address issues based on stage of quit attempt for 12 weeks.

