## Feasibility and Acceptability Measures

Feasibility and acceptability will be assessed using session attendance (recorded as a continuous variable ranging from 1 to 4 study sessions) and retention (coded as a dichotomous

variable with participants who complete the 24-week session characterized as completers and those not attending the final session as non-completers). The Helping Relationships subscale of the Processes of Change Questionnaire will be used to examine satisfaction with PNs in the active condition. CSQ-8 will be used to compare treatment satisfaction by condition.

Efficacy Measures: The main outcome analyses and effect size estimates will be based upon biochemically verified 7-day point-prevalence abstinence at 4-, 12-, and 24-week follow-ups. Pointprevalence abstinence will be verified by saliva cotinine radioimmune assay analysis (cutoff value of < 15 ng/ml) for stated abstinence of 7 days or longer in those not currently using NRT or other nicotinecontaining products. Self-report will always be overridden by objective verification of abstinence in the final analyses. Timeline Followback (TLFB) will be used to assess Quitline contact, enrollment in smokefree.gov, prescription receipt for cessation pharmacotherapy, quit attempts (defined as a 24hour period of no smoking), and continuous abstinence. Breath samples for CO will be obtained at each study visit.

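### Adherence is measured only in participants who set a quit date, a step after randomization that PNSS-S aims to increase, so the planned arm contrast on adherence is not a randomized comparison

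*Combined protocol and SAP*

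**What the plan says.** The combined protocol and SAP makes adherence an arm comparison. Under Methodology: "We will examine the effect of PN on Quitline contact, quit attempts, adherence to pharmacotherapy", followed by other outcomes. The same section plans preliminary effect sizes for mechanisms of change and says the data will be used to plan a full-scale trial. Aim 2 compares the arms on mechanisms.

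Under Mechanisms of PNSS-S Effect, the measurement is limited to a subset: "In participants who set a quit date, adherence to pharmacotherapy will be measured via participant self-report and pharmacy refill report at each study session".

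The two arms reach that subset, and the medication, by different routes:

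- Description and Purpose of the Project: "a PN may encourage the smoker to set a quit date, adhere to smoking cessation medication therapy".
- Standard Care Condition: "Those willing to set a quit date will be instructed to call their physician for cessation medication". Those not ready are left to contact their doctor later.
- PNSS-S Condition: the PN acts as go-between, "facilitating the acquisition of the medication by coordinating with the" participant's doctor, and checks coverage and pickup. Those not ready keep discussing barriers with the PN over the following weeks.

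Prescription receipt is recorded without restriction to setters, under Feasibility and Acceptability Measures: "Timeline Followback (TLFB) will be used to assess Quitline contact, enrollment in smokefree.gov, prescription receipt for cessation pharmacotherapy, quit attempts".

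The Data Analysis Plan names "Tests of the effect of treatment condition on Quitline usage, quit attempts, and on 7-day point-prevalence abstinence" by GEE. Its mechanisms part is motivated by two variables: "increased social support and self-efficacy for quitting are important outcomes in and of themselves". Adherence is not named in either place.

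**The concern.** Smokers enter whatever their readiness to quit, and they are randomized after the baseline interview, before the nurse visit at which a quit date is discussed. Some will never set a date, and the share who do is something PNSS-S is designed to change. A comparison of adherence among setters therefore conditions on a consequence of treatment. If the PN brings less committed smokers into the subset, PNSS-S setters may adhere less on average although nobody's adherence was harmed. If the PN instead secures prescriptions that SC setters never obtain, PNSS-S setters may appear to adhere more although nobody takes a prescribed drug more faithfully.

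The plan's general safeguards do not reach this. The intention-to-treat sentence supplies no adherence value for a non-setter, because none is collected by design. The missing-equals-smoking rule concerns smoking outcomes. Receipt on the Timeline Followback (TLFB) shows access, not medication-taking, and does not undo the selection.

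At stake is one of the effect sizes meant to inform the next trial. Obtaining medication and improving adherence are both stated PN functions.

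**Working it through.** The plan gives no figure for adherence, date-setting or prescription, so there is none to reproduce. The only documented input is 36 per arm (Methodology). Every rate below is an assumption.

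**1. Selection alone.** Let s0 and s1 be the shares setting a date in SC and PNSS-S, a the adherence of those who would set a date in either arm, and i the adherence of those who set one only under PNSS-S. With no effect on any individual's adherence and equal access:

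false difference = (s0·a + (s1 - s0)·i)/s1 - a = (s1 - s0)(i - a)/s1

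- The sign is the sign of i - a, which the documents do not give.
- The difference is 0 if the setting rates are equal or if i = a.
- With s0 = 40%, s1 = 60%, a = 0.60, i = 0.30: 0.20 × (-0.30)/0.60 = -10 points.
- Over s0 = 30% to 50%, an increase of 0 to 30 points and i = 0.30 to 0.60 (a = 0.60), it runs from 0 to -15 points.

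**2. Selection and access together.** Let p be the share of setters prescribed.

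- SC: s = 0.50, p = 0.30 to 0.70, a = 0.60.
- PNSS-S: s = 0.65, p = 0.90, mean adherence if prescribed = (0.50 × 0.60 + 0.15·i)/0.65. This is 0.531 for i = 0.30 and 0.60 for i = 0.60.

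PNSS-S minus SC, in points:

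| Analysis set | i = 0.30 | i = 0.60 |
|---|---|---|
| Those prescribed | 53.1 - 60 = -7 | 0 |
| All setters, no prescription = 0 | 47.8 - (18 to 42) = +30 to +6 | 54 - (18 to 42) = +36 to +12 |
| All 36 per arm, no medication = 0 | 31.05 - (9 to 21) = +22 to +10 | 35.1 - (9 to 21) = +26 to +14 |

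With p = 0.90 in both arms and i = 0.30, the three rows become -7, 47.8 - 54 = -6, and 31.05 - 27 = +4.

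The same participants thus give different answers, even in sign, depending on who is counted and how a setter without a prescription is scored. Only the last row compares the groups as randomized, and it measures uptake and adherence together.

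**3. Precision.** Numbers prescribed are 36 × 0.65 × 0.90 = 21.1 in PNSS-S and 36 × 0.50 × p = 5.4 to 12.6 in SC. With an assumed SD of 35 points, the 95% half-width is 1.96 × 35 × √(1/21.1 + 1/n), which is 33 points at n = 5.4 and 24 at n = 12.6. The -7 is small beside that.

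**4. Prescription receipt, everyone randomized.** PNSS-S 0.65 × 0.90 = 58.5%; SC 0.50 × p = 15% to 35%. The exact power of an uncorrected chi-square test (36 per arm, two-sided 0.05) is about 98% to 51%. This concerns access and says nothing about the size of the adherence bias.

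**The case against.** The strongest reply has four parts.

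*The harm is assumed.* A reader might infer that the plan will make PNSS-S look worse on adherence. The documents do not support that. With unequal access, the all-setters figures above are positive. They turn negative only with equal access and extra setters who adhere less well. If the extra setters adhere like the rest, the selection bias is zero. This stands: the direction is open and the size unknown. An estimate whose bias can go either way is still not a randomized one.

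*The pilot disclaims precision.* The sample-size paragraph expects large standard errors, and the mechanisms paragraph tests only plausibility. This also stands and limits the importance. It does not remove the selection, which a larger trial with the same definition would inherit.

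*The gaps may be filled elsewhere.* A reader might infer that adherence has no score and no analysis at all. That goes too far. The generic model fitted for each mediator can be read to cover adherence, and the attached measures are not available here. The Pharmacotherapy section also expects every setter to be prescribed a drug. Still, that model needs a baseline-to-week-4 slope and fits adherence poorly, because current users of cessation medication are excluded. The expectation of a prescription is not a scoring rule. These are missing details that add to the main point; they do not carry it.

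*The remedy changes the question.* Scoring 0 for no medication mixes uptake with adherence. In the i = 0.60 case it shows +26 to +14 although adherence among those prescribed is identical. This is correct, so the outcome must be named for what it is and adherence among those prescribed kept in the report. Non-setters could largely be scored 0 from TLFB receipt and the rule tying medication to a quit date, but asking everyone directly is more secure.

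**Conclusion.** The point holds. The plan intends an arm contrast on adherence and restricts measurement to a subset formed after randomization, which the intervention works to enlarge and within which access to medication differs by arm. That contrast is not protected by randomization and can be biased in either direction.

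Its size cannot be derived from the documents. The selection term of 0 to -15 points and the figures in the table rest wholly on assumed rates. The negative sign of the selection term rests on the further assumption that the extra setters adhere less well.

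The consequence is limited to a secondary mechanism estimate in a pilot. A reader might infer that the efficacy result is also compromised. It is not: the abstinence GEE includes all randomized participants and does not depend on this measurement. The change is worth making because it is cheap and because medication use in non-setters may be hard to recover if it is never asked.

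**What to change.** Under Mechanisms of PNSS-S Effect, record days of cessation-medication use since the previous assessment for every randomized participant at weeks 4, 12 and 24, by self-report checked against refill. Score 0 when no medication was used. A missed visit is missing data, not a 0.

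In the Data Analysis Plan:

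- Make the randomized comparison medication use, described as uptake and adherence combined, in all 36 per arm and adjusted for sex as in the other analyses.
- Add a comparison of TLFB prescription receipt in the same 36 per arm.
- Report adherence among those prescribed by arm, with the numbers who set a date and who were prescribed, labelled as a non-randomized descriptive estimate.
- If medication use is examined as a mediator, use the week-4 value in place of a baseline-to-week-4 slope.

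The cost is one extra self-report item per follow-up visit, some wording and a little analysis, with no new visits. The remaining drawback is that the randomized outcome does not separate adherence from uptake. The descriptive figure addresses that only with the caveat it carries.
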